## STUDY PROTOCOL OVERVIEW

Visit:	Schedule	Investigation:
Visit 0 (pre-study)	30 days prior to starting Controlled Ovarian Stimulation	
 
• Verification of inclusion criteria
 
• Informed consent form
 

Visit 1	From day 1 o - 3 o of the cycle for ovarian stimulation	
 
• Signature of informed consent
 
• Blood simple for Estradiol levels
 
• Vaginal scan and follicular count
 
• Height and weight
 
• Randomization
 

### STUDY GROUP:

Visit:	Schedule	Investigation:
Start of treatment (S1)	Beginning of gonadotrophins administration (according to randomization): 
 
- 5o day of the cycle
 
- 7o day of the cycle
 
- 9o day of the cycle
 
- 11o day of the cycle
 
- 13o day of the cycle
 
	
 
• Starting dose: identical to the dose used in the control cycle.
 
• S1 refers to the first day of ovarian stimulation
 

Visit 2 (1st control)	On the 5 o -6 o of ovarian stimulation (S5-S6)	
 
• Transvaginal scan and folliculometry
 
• Starting of GnRH antagonist (Cetrotide® )
 
• Blood samples: Estradiol, Progesterone, FSH, LH
 

Follow-up	Every 24-72 hours	
 
• Transvaginal scan and folliculometry
 

Visit 3 (Agonist)	On the day of triggering (final follicular maturation)	
 
• Transvaginal scan and folliculometry
 
• Administration of 2 ampules of Decapeptyl® (0,2 mg triptorelin acetate) with follicles 18-20 mm.
 

Visit 4 (Egg collection)	Egg collection	
 
• Transvaginal egg retrieval 36 hours after triggering.
 
• Blood samples: Estradiol, Progesterone, FSH, LH.
 

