### 2. Methods

#### 2.1 Design

This is a prospective, open, randomized, self-comparative, pilot study. The type of protocol (antagonist/GnRH-a trigger) and gonadotrophin type/dose will be identical between the study and control groups; except for the day of starting the OS process in relation to the last menses. The control cycle includes a conventional previous cycle underwent by the same population in the six previous months of the randomization, thereby, decreasing inter-subject variability. The eggs from the study group will be

inseminated using IVF conventional / ICSI using partner's sperm. Fertilization will be evaluated 18-24 hours later.

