## 2.4 Statistical analysis plan and sample size

The sample size was calculated assuming a non-inferiority margin of 5 eggs SD 6.7 (based on: Devroey et al. Hum Reprod. 2009;24(12):3063-72). A unilateral alpha level of 0.05 was established. With the aim to show that the difference in the mean number of collected eggs will not exceed 5, a statistical power of 80% required 30 patients per group (1:1 allocation, total sample: 60). Statistical analysis was performed using t-student test for continuous variables and chi-square test for categorical parameters. A P value of <.05 was considered significant.

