### CONTROL GROUP:

A previous cycle underwent by the egg-donor within 6 months previously to the inclusion in the study group for the ROSE trial; in brief:

- Day 1-2 of the cycle. Transvaginal scan and follicular count. Starting of gonadotrophins 150-225 IU (Fostipur®) according to BMI and AFC (D1 of ovarian stimulation).
- Day 5-6 of ovarian stimulation. Transvaginal scan and folliculometry. Starting of GnRH antagonists (Cetrotide®) beginning with a dominant follicle  $\geq 14$  mm.
- Follow-up every 24-72 hours.
- Administration of 2 ampules of Decapeptyl® (0,2 mg triptorelin acetate) with follicles 18-20 mm to induce the final follicular maturation.
- Transvaginal egg retrieval 36 hours after triggering

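### Does the missing follicle-size condition for starting the antagonist in the study cycle mix the start-day comparison with a second rule?

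*Combined protocol and SAP*

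**What the plan says.** Three places in the combined protocol and SAP bear on this.

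- **Study Group, Visit 2.** The visit falls on the fifth to sixth day "of ovarian stimulation (S5-S6"). It lists a transvaginal scan with folliculometry, then "Starting of GnRH antagonist (Cetrotide" (product name), then blood samples. No follicle size is given for the antagonist.
- **Control Group.** The corresponding line opens "Day 5-6 of ovarian stimulation. Transvaginal scan and folliculometry" and continues "Starting of GnRH antagonists (Cetrotide®) beginning with a dominant follicle" of at least 14 mm. The next line is "Follow-up every 24-72 hours".
- **2.1 Design.** "The type of protocol (antagonist/GnRH-a trigger) and gonadotrophin type/dose will be identical between the study and control groups", with the day of starting stimulation as the exception. The antagonist-start criterion is not mentioned either way.

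The control is an earlier conventional cycle of the same donor, completed within the six months before randomization.

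**The concern.** The study is meant to show what a later stimulation start does to egg yield. If the antagonist goes by calendar day in the study cycle and by follicle size in the control cycle, two things change between a donor's cycles. A difference in eggs, mature eggs, stimulation days or FSH use could then reflect either one.

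Using the same donor twice would not help, because the rule would differ in the same direction for every donor. Randomization would not help either: it assigns start days within the study cycle (days 5 to 13) and has no part in the comparison with the earlier control cycle.

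The study table does carry a follicle size for the trigger, "Administration of 2 ampules of Decapeptyl® (0,2 mg triptorelin acetate) with follicles 18-20 mm", so its silence on the antagonist can look deliberate.

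**Working it through.** **Step 1: set the sections side by side.**

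| Item | Study Group | Control Group | 2.1 Design |
|---|---|---|---|
| Gonadotrophin product | not named | named | type identical |
| Starting dose | same as the control cycle | 150-225 IU | dose identical |
| Visit for antagonist start | S5-S6, with folliculometry | stimulation day 5-6, with folliculometry | protocol type identical |
| Follicle size for antagonist | not stated | at least 14 mm | not addressed |
| Follow-up | every 24-72 hours | every 24-72 hours | not addressed |
| Follicle size for trigger | 18-20 mm | 18-20 mm | not addressed |
| Retrieval after trigger | 36 hours | 36 hours | not addressed |

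The study table leaves out two details that the control section gives: the gonadotrophin product and the antagonist follicle size. Section 2.1 supplies the first. The second may be an omission of the same kind. Nothing in the table says that the antagonist starts whatever the follicle size.

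**Step 2: when the two scans fall.** Stimulation day *k* is cycle day (start day + *k* − 1).

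- Study, earliest start (day 5): S5-S6 is cycle day 9-10.
- Study, latest start (day 13): S5-S6 is cycle day 17-18.
- Control, start on day 1-2: stimulation day 5-6 is cycle day 5-7.

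Each donor therefore has two scans at different points of the cycle, and the leading follicle may differ between them.

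**Step 3: which cycles a second rule could touch.** Suppose the study cycle really had no size condition. The rule then alters management only in study cycles with a leading follicle below 14 mm at S5-S6, since only those would have waited under the control rule. In all other study cycles the two rules coincide.

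A wait of one follow-up interval (24-72 hours, so 1-3 days) in the *control* cycle does not measure this. It could arise under one shared rule, because the control scan comes earlier in the cycle. Any such shift in antagonist timing would be a consequence of start day, which is what the study compares. The 1-3 days are therefore not a measure of bias.

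**Step 4: can section 2.4 size the effect?** Its inputs are a "non-inferiority margin of 5 eggs SD 6.7", one-sided alpha 0.05, 80% power and 30 per group. For two independent groups (normal approximation):

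- n = 2 × 6.7² × (1.645 + 0.842)² / 5² ≈ 22.2, so 23 per group. The stated 30 is not reproduced; it errs on the large side, a separate matter.
- With 30 per group, SE = 6.7 × √(2/30) = 1.730, and power = Φ(5/1.730 − 1.645) ≈ 89%.
- With an assumed shift of 0.7 eggs against the study cycle, power = Φ(4.3/1.730 − 1.645) ≈ 80%.
- With an assumed shift of 0.7 eggs in its favour, one-sided error at the margin = Φ(0.7/1.730 − 1.645) ≈ 11%.

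The 0.7 has no source in the documents: it is simply the shift that brings power down to 80%. The same lines would describe any unspecified bias of that size, so they say nothing about the antagonist rule. They also assume independent groups, whereas each donor is her own control, and the within-donor correlation is not given.

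**The case for a change.** The best case for acting is that abbreviation is not the obvious reading. The study table keeps the trigger size and the retrieval interval, both matching the control section, and the section that carries the 14 mm condition is the one introduced as a brief summary. Section 2.1 does not settle the matter, because it names protocol type and gonadotrophin type and dose but not the antagonist criterion. The plan also does not say that antagonist start day will be reported, so a reader might be unable to check afterwards. Stating the rule would cost little.

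Much of this stands. The texts differ, and the documents neither confirm nor exclude two rules. What does not stand is the step from a missing table entry to a confounded comparison. That step needs a second rule in practice, a share of study cycles below 14 mm at S5-S6 and an effect on egg number, and the documents supply none of these. Section 2.1 also makes no blanket claim that start day is the only difference, so there is no such claim to withdraw.

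**Conclusion.** No change to design, sample size or analysis follows. This is a missing detail in one table row. The sections should be reconciled in wording, and the clinical rule is for the sponsor's clinicians. The rule behind the control cycles is already a matter of record, since those cycles were complete before randomization.

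Analysts can deal with the point when reporting: give antagonist start day and leading follicle size by cycle where recorded and, if the rules turn out to have differed, describe the contrast as start day plus antagonist-start rule. Follicle scans are already scheduled in both cycles, so no new procedure is needed.

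Size: zero under one shared rule; not derivable from the documents under two. This rests on two assumptions: that the study table can fairly be read together with section 2.1, and that scan and medication records exist for the control cycles. If the sponsor confirmed that two rules were used, the interpretation of the result would have to say so.

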### CONTROL GROUP:

A previous cycle underwent by the egg-donor within 6 months previously to the inclusion in the study group for the ROSE trial; in brief:

- Day 1-2 of the cycle. Transvaginal scan and follicular count. Starting of gonadotrophins 150-225 IU (Fostipur®) according to BMI and AFC (D1 of ovarian stimulation).
- Day 5-6 of ovarian stimulation. Transvaginal scan and folliculometry. Starting of GnRH antagonists (Cetrotide®) beginning with a dominant follicle  $\geq 14$  mm.
- Follow-up every 24-72 hours.
- Administration of 2 ampules of Decapeptyl® (0,2 mg triptorelin acetate) with follicles 18-20 mm to induce the final follicular maturation.
- Transvaginal egg retrieval 36 hours after triggering

### **Main outcome**

To evaluate and compare the total number and MII rate of eggs collected after beginning the ovarian stimulation in different moments of the follicular phase vs standard protocol.

### **Secondary outcomes**

To evaluate differences with regards to the duration of the ovarian stimulation, FSH consumption and fertilization rates between groups.
